4.7 Study Phases

The study will be conducted in three phases as subjects are consented and evaluated for eligibility, treated and followed until study exit:

Phase 1 - Pre-Admission Evaluation/Patient Consent

Phase 2 – Baseline/Treatment

Phase 3 – Follow-Up 90 Days (+/- 15 days) Post-Procedure / Study Exit

The assessments to be performed during each phase are listed in Table 1.

Pre-Admission Evaluation/Patient Consent

Patients presenting with symptoms associated with nasal airway obstruction will be approached with the study and asked if they are willing to volunteer participation. Patients will initially be asked about duration of symptoms and conservative measures used for their condition. Any known concomitant nasal conditions and past nasal surgeries will be discussed to understand if they are potential candidates for the study.

Table 1. Schedule of Assessments

Assessments	Screening / Evaluation	Baseline/Study Procedure	Immediately Post-Treatment	90 day Follow-Up / Study Exit (+/- 15 days)
Informed Consent	X			
Demographics and Medical History	X			
Physical Exam and Vital Signs		X		
Medication Review		X		X
SF-36 Quality of Life Questionnaire		X		X
NOSE Score	X			X
Study Procedure		X		
Endoscopic Assessment of treatment area (with representative still photographs)		X	X	X
Cone beam CT scan (clinical or research)		X		X
Sino-Nasal Outcome Test (SNOT-22)		X		X
Peak Nasal Inspiratory Flow (PNIF)		X		X
Visual Analog Scale (VAS) of nasal obstruction		X		X
Adverse Event review			X	X
Pregnancy test (if female of child bearing potential)		X		

Informed Consent

Informed consent will be obtained as outlined in 21 CFR Part 50 and the Good Clinical Practice: Consolidated Guidance (ICH, April 1996).

A research study member at the approved study site will speak with the study candidate about the purpose of the study and investigational research. Explanation of the study background, study procedure, follow-up visit schedule, and study procedure risks and benefits will be

reviewed in detail with the patient. Patients will be given the time they need to read through the study information and informed consent document and to ask as many questions as necessary to make them comfortable with the study and the requirements. A patient willing to participate after undergoing the informed consent process will then be asked to sign the consent form and given a copy. The original will be kept on file.

For those potential candidates who agree to participate in the study by signing the IRB approved Informed Consent Form (ICF), a baseline evaluation will be conducted. Subjects will be considered enrolled once they arrive at the study clinic to undergo the procedure. At this time a subject identification number will be assigned along with the subject binder.

During the baseline and follow-up visits, the procedures listed below will occur

1. Endoscopic examination (video and pictures), Lund-Kennedy endoscopic scores
2. Peak nasal inspiratory flow
3. Cone beam CT scan (clinical CT at baseline; clinical or research CT at 90-day follow-up visit)
4. Nasal Obstruction Symptom Evaluation (NOSE) scale
5. Sino-Nasal Outcome Test (SNOT-22)
6. Visual analogue scale (VAS) rating severity of nasal obstruction
7. Computational modeling of nasal airflow based on CT scan of each visit.

During the baseline visit, data collection will be performed first, and then the Aerin Vivaer™ Treatment will be provided in the clinic by the physician. The styluses used in this study will be manufactured and supplied by the sponsor.

During the treatment, 0.5 ml of local anesthesia (lidocaine 1% with epinephrine 1:100,000) will be injected into the target tissue. The Vivaer stylus will be inserted into the nose and the electrode-containing tip will be positioned against the target tissue.

Subjects will have both nasal valves treated in a single study procedure session. Each nostril will be treated at up to 3 non-overlapping positions along the upper lateral nasal valve region.

Treatment settings to be used are:

Temperature.....60°C
Power 4 Watts
Treatment Time 18 secs
Cooling Time 12 secs

Accurate positioning will be confirmed by observing the temperature change on the RF generator screen as the stylus tip comes in contact with the target tissue.

No repeat ("touch-up") procedures will be permitted during the 90-day follow-up period.

Immediate Post-Procedure Care (prior to leaving the clinic)

At the discretion of the physician, the following care and instructions may be provided:

- Apply petroleum jelly to the treatment area as needed.

- The patient should be instructed not to manipulate the treatment site for 24 hours with the exception of any necessary hemostasis.

Study subjects will be reminded of their next follow-up visit and will be scheduled within the study window (90 ± 15 days).

Adverse events (AEs) may occur during the treatment phase or during the follow-up phase. Adverse events occurring during the baseline assessment will be documented in the subject's medical record but will not count as related to the device or procedure. Each adverse event will be recorded and judged by the Investigator as to its relationship and level of relatedness to the device and/or procedure. In addition, the Investigator will identify the date of onset, severity and duration. All adverse events will be monitored until they are adequately resolved or explained.

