4.6 Measurement / Instrumentation

Endoscopic Examination

Patients will receive endoscopic examination as part of their standard clinical care. The severity of disease will be scored based on endoscopic examination (Lund-Kennedy endoscopic scores).

Study Procedures

Each visit is expected to last 2-3 hours and may include the following procedures. (These procedures are routinely performed for research purposes; however, none of them should be considered standard clinical care. The differences will be explained to the participants during the consent process.)

1. All participants will be asked to fill out a medical history questionnaire, as well as the Sino-Nasal Outcome Test (SNOT-22) questionnaire, the NOSE score and the Visual Analog Scale for nasal obstruction. The SNOT-22 and NOSE are two commonly used validated outcome questionnaires to evaluate change in rhinosinusitis and/or nasal obstruction symptoms in patients. The VAS is a self-rating of nasal obstruction on a linear scale (range 0-10; 0 being completely clear and 10 being completely blocked) using both nostrils and then with the left and right nostril separately.
2. Peak nasal inspiratory flow: A mask attached to a spirometer is fitted tightly on each subject's face without touching the nose. The subject is instructed to inhale as strongly as possible, and the peak flow rate is then recorded. The test will be repeated three (3) times and the results averaged. For unilateral recording, one nostril is blocked with a tape, so that the subject can only inhale through the other nostril.

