5. Adverse Event Evaluation – Subjects will be asked about possible side effects or adverse experiences related to the study procedure. All events will be documented on the proper Adverse Event Log and Adverse Event Case Report Form. Anticipated observations related to the study procedure will be tabulated, but will not be categorized as adverse events unless they require mitigation by the treating physician or are greater in severity, duration or degree of incidence than anticipated. Refer to Table 2 for a listing of anticipated observations as well as anticipated frequency, severity and duration.

7. Medications – Updates to current medications or any new or changed medications will be requested at each follow-up visit. The medication log will be updated to reflect any changes. In addition, any medications required as a result of intervention related to the study procedure will be documented and will correlate with the Adverse Event Case Report Form.
8. General Health Survey Subject will be asked to complete the SF-36 before and after treatment. The SF-36 is one of the most widely used generic measures of health-related quality of life and has been shown to discriminate between subjects with different chronic conditions and between subjects with different severity levels of the same disease. The SF-36 has also demonstrated sensitivity to significant treatment effects in a variety of patient populations.

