6.0 STUDY WITHDRAWAL

Subjects may be terminated or withdrawn from the study for the following reasons:

- Voluntary withdrawal – the subject voluntarily chooses not to further participate in the study
- *Lost to follow-up – the subject is more than one month late (beyond the late visit window) to a study visit and 3 documented attempts to contact the subject are unsuccessful. A subject who misses a study visit but attends a subsequent visit will no longer be considered lost to follow-up.
- *In the physician's opinion, it is not in the best interest of the subject to continue study participation.
- Subject death.

**Where possible, subjects will be followed for safety to study completion. Safety follow-up will include a review of adverse events (AEs). A safety follow-up assessment may be performed either via a phone or email contact or a physician visit.*

Any study subject who does not attend the scheduled follow-up visit should be contacted by site personnel to determine the reason for the missed appointment. The reason for the missed visit should be determined and documented in the subject's study records. All subjects enrolled

(including those withdrawn or lost to follow-up) shall be accounted for with appropriate documentation.

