25.0 DEFINITIONS AND ACRONYMS

Adverse Events

Adverse Event (AE) – any untoward medical occurrence in a subject (ISO 14155).

NOTE: This definition does not imply that there is a relationship between the adverse event and the device under investigation.

Serious Adverse Event (SAE) – an adverse event that (ISO 14155):

- led to a death,
- led to a serious deterioration in the health of the subject,
- resulted in a life-threatening illness or injury,
- resulted in a permanent impairment of a body structure or a body function,
- required hospitalization or prolongation of existing hospitalization,
- resulted in medical or surgical intervention to prevent permanent impairment to body structure or function,
- led to fetal distress, fetal death, a congenital abnormality, or birth defect.

Adverse Device Effect (ADE) – any untoward and unintended response to a medical device (ISO 14155)

NOTE: This includes any event resulting from insufficiencies or inadequacies in the instructions for use or the deployment of the device. This definition also includes any event that is a result of user error.

Serious Adverse Device Effect (SADE) – an adverse device effect that has resulted in any of the consequences characteristic of a serious adverse event or that might have led to any of these consequences if suitable action had not been taken or intervention had not been made or if circumstances had been less opportune (ISO 14155).

Anticipated Adverse Device Effect (AADE) – an adverse device effect which by its nature, incidence, severity or outcome has been previously identified in the previously identified in nature, severity, or degree of incidence in the investigational plan or application

Unanticipated Adverse Device Effect (UADE) – any serious adverse effect on health or safety or any life-threatening problem or death caused by, or associated with, a device, if that effect, problem, or death was not previously identified in nature, severity, or degree of incidence in the investigational plan or application (including a supplementary plan or application), or any other unanticipated serious problem associated with a device that relates to the rights, safety, or welfare of subjects (21 CFR 812.3.s and ISO 14155).

NOTE: The occurrence of a diagnostic or elective surgical procedure for a pre-existing condition, unless the condition becomes more severe or increases in frequency, would not be considered procedure or device-related.

Adverse Device Effect (ADE)

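### Minor safety gap: the visible plan has no pregnancy check before a research-only CT at day 90, 75–105 days after the only scheduled test

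*Combined protocol and SAP*

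**What the plan says.** The schedule of assessments (section 4.7, Table 1) contains the row "Pregnancy test (if female of child bearing potential", with a single mark under the baseline/procedure visit. The 90-day cell of that row is empty. The cone beam CT row is marked at both visits.

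Section 4.7 also states which kind of CT belongs to which visit: clinical at baseline, and clinical or research at 90 days. Section 4.6(3) describes the research scan as non-clinical in purpose and as something a subject may receive. Recruitment is to favour patients who already have a clinically prescribed sinus CT, which then serves as the baseline scan. A clinically needed post-treatment CT is to be timed for the second visit. Together these measures are meant to hold research scans to one per patient. The dose is given as roughly 12% of that of a conventional head CT.

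Pregnancy or lactation is exclusion 6 in section 4.4, where the list is framed as a bar to enrolment. The only other related text is in the section 25.0 definition of a serious adverse event, which covers an event that "led to fetal distress, fetal death, a congenital abnormality, or birth defect".

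**The concern.** The schedule tests for pregnancy at the visit where the CT is clinical, and not at the visit where it may be done only for research. A woman who conceives after baseline and does not know it could have a scan that serves no clinical purpose for her, with nothing in the schedule to prompt a check. Section 4.6(3) itself sets out to avoid unnecessary radiation, so the omission works against the plan's own aim.

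What is at stake is participant safety on a small scale. The NOSE and VAS endpoints, the repeated-measures comparison and the correlation and classification analyses are not affected.

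**Working it through.** The plan gives no figure of its own to reproduce. The check sets the relevant texts side by side and works out one interval.

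**1. Where the research scan falls.** Table 1 labels the CT row as clinical or research at both visits, so the table alone does not exclude a research scan at baseline. Sections 4.6(3) and 4.7 do settle it: the baseline CT is clinical. With at most one research scan per patient, that scan belongs to day 90. Section 4.7 lists the CT among the procedures that will take place at follow-up, so a subject with no clinical need for a post-treatment CT would have a research scan if she is scanned. If a research scan were nevertheless done at baseline, the test at that visit would cover it and the limit of one would rule out a second at day 90.

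**2. Interval from test to scan.** Data collection and treatment share the baseline visit (section 4.7), so the test and day 0 coincide. The follow-up window is 90 ± 15 days.

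- Earliest: 90 − 15 = 75 days; 75 / 7 = 10.7 weeks.
- Latest in window: 90 + 15 = 105 days; 105 / 7 = 15.0 weeks.

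A late visit could lengthen this, because section 6.0 treats a subject as lost only when more than one month beyond the window.

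**3. Count of checks.** Scheduled pregnancy tests in Table 1: 1, at baseline. In the 90-day column: 0. The visible text contains no contraception requirement, no pregnancy-specific withdrawal rule and no statement that exclusion 6 is re-applied at follow-up.

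**4. Other routes that might catch a pregnancy at day 90.**

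| Route | What the plan says | Limit |
|---|---|---|
| Medical history | Section 4.6: "Each visit is expected to last 2-3 hours and may include the following procedures"; item 1: "All participants will be asked to fill out a medical history questionnaire" | Table 1 marks medical history at screening only; the questionnaire's content is not shown |
| Medication review | Section 4.6(7): "Updates to current medications or any new or changed medications will be requested at each follow-up visit" | Could reveal a pregnancy only indirectly |
| Adverse event review | Section 4.6(5): "Subjects will be asked about possible side effects or adverse experiences related to the study procedure" | The question concerns the procedure, although section 25.0 defines an adverse event broadly as "any untoward medical occurrence in a subject" |
| Physician withdrawal | Section 6.0: withdrawal if, in the physician's opinion, "it is not in the best interest of the subject to continue study participation" | Requires the physician to know |

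Any of the four might bring out a pregnancy the woman knows of and mentions. None is a test, and none is tied to the scan. An unrecognised or undisclosed pregnancy can pass all four.

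**5. Scale.** At most one research scan per patient and at most 20 patients, both sexes, aged 18 to 75. The number of women of child-bearing potential who would have a research scan is not given, and neither is a fetal dose. No risk can therefore be calculated; 20 is the enrolment cap and not an estimate of those affected.

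**The case against.** The strongest reply is that this is an absence found in an incomplete text. Consent pages, a natural place for radiation and pregnancy warnings, were removed before review. Sections 9.0 and 10.0 bind the study to IRB requirements and conditions that are not shown. The numbered list in section 4.6 goes from item 5 to item 7; item 6 is not in the supplied text, and its content, if it ever existed, is unknown. A precaution could sit in any of these places. This stands as a limit on the claim: it cannot be said that subjects are unprotected, only that the visible protocol does not protect them at this step. It does not remove the point, because Table 1 is the stated schedule and its 90-day pregnancy-test cell is empty.

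Second, there is no contradiction with exclusion 6. It is an entry criterion, and one test before anaesthetic injection and treatment fits it. That is right, and no contradiction is alleged.

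Third, 75 to 105 days is time elapsed and not risk. Many pregnancies that began early in that interval would be recognised by day 90, so the period in which one could go unnoticed is shorter. That also stands. Harm further requires conception after baseline, no recognition or disclosure, and a research rather than a clinical scan, all at a low stated dose. These conditions explain the low severity.

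**Conclusion.** The concern holds as a minor participant-safety gap. On the visible text, a research-only CT can be done 75 to 105 days after the only scheduled pregnancy test with no check beforehand. The conclusion rests on reading sections 4.6(3) and 4.7 as making the baseline CT clinical, and on no safeguard being present in the material that was not available. The probability of exposure and any fetal harm cannot be quantified from the documents. Confidence is medium because of the unseen material.

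**What to change.** In the 90-day column of Table 1, add a pregnancy test conditional on child-bearing potential and on the CT being a research scan, to be done before the scan. In section 4.6(3), add that the research CT is not performed if the subject is known or found to be pregnant.

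A lighter alternative is a recorded pregnancy question before the scan, with a test if pregnancy is suspected. It mirrors the known-or-suspected standard of exclusion 6 but would miss an unrecognised pregnancy, so the test is preferable.

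The cost is one conditional table entry and one sentence, using a test the study already performs. The burden is one simple test per affected woman and possibly an occasional missing day-90 airflow model. If the consent form or the IRB already requires such a check, entering it in Table 1 costs almost nothing.

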4.8 Internal Validity

The participating physicians will ensure that the recruitment material is well distributed to all potential subject/patient populations. In the recruitment process, they will specifically emphasize to all potential subjects/patients that whether or not they agree to participate will not have any impact on their continuing treatment and interactions at the Department of Otolaryngology, The Ohio State University School of Medicine.

4.9 Data Analysis

Treatment effectiveness

Outcome variables: patient's ratings of nasal obstruction via a VAS and NOSE score as well as the SNOT-22 questionnaire and peak inspiratory flow rate. One-way ANOVA with repeated measures will be used to compare post-treatment vs. baseline measurements and determine the effectiveness of the treatment.

Hypothesis:

Nasal valve region airflow and airflow induced cooling is critical for patients' subjective nasal patency.

Many publications suggest that sensory feedback is as important to perception of nasal obstruction as nasal resistance. For example: Topical or oral application of menthol produces the illusion of decongestion and improved nasal airflow without actually altering nasal resistance¹⁰. Topical application of local anesthetics results in an artificial sensation of nasal obstruction, presumably due to blocking of the trigeminal afferents¹¹.

The Ohio State University (OSU) staff have published a series of studies^{6,12,13} with individualized Computational Fluid Dynamics models and demonstrated that nasal cooling during breathing at the nasal valve region and the nasal trigeminal nerve sensitivity are key to the perception or absence of nasal obstruction. The combination of these variables can predict the subject's ratings (excellent, normal and moderately obstructed) with 89.3% success. It is likely that nasal valve width and shape may have an optimal range in order to achieve both low nasal resistance and high regional mucosal cooling (see Fig. 5). This study will examine a broad list of factors that may contribute to patients' subjective outcomes, not just limited to nasal resistance alone, that include CFD simulation of nasal airflow, mucosa cooling and mucosa sensitivity responding to that cooling.

[figure not shown]

Figure 5. Computational simulation of nasal cooling

- a) high regional cooling, no complaints
- b) low nasal cooling with moderate ratings of nasal obstruction

Spearmen correlation and multiple regression will be used to screen for independent variables that significantly correlate with dependent variables, as well as potential non-linear relationships between the variables. Other potential confounding factors (e.g., age, duration of the disease, smoking history) will also be examined. The Holm Bonferroni correction will be applied to control for multiple comparisons. Finally, statistical learning methods such as linear discrimination analysis (LDA) and logistic regression will be applied for classification and discrimination of patient symptom categories (e.g., symptom-free, moderate and severe nasal obstruction) based on significant independent variables.

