1.0 PROTOCOL SYNOPSIS

Study Title:	A Prospective, Non-Randomized Study to Evaluate Treatment Outcome of Nasal Airway Obstruction Using the Aerin Medical Vivaer™ Stylus
Study Device:	Aerin Medical Vivaer Stylus
Device Description:	The Vivaer Stylus is a disposable handheld device capable of delivering bipolar radiofrequency energy to tissue.
Proposed Indication:	The Vivaer Stylus is indicated for the treatment of nasal obstruction by the modification of submucosal tissue including cartilage in the internal nasal valve area.
Study Objective:	The main objective of this research is to evaluate the outcome of treating nasal airway obstruction with the Aerin Medical Vivaer Stylus
Study Design:	Prospective, non-randomized study to evaluate treatment outcome of nasal airway obstruction using the Aerin Medical Vivaer stylus
Subject Population:	Male and female subjects who present with symptoms associated with chronic nasal obstruction
Study Procedures:	Subjects will have both nasal valves treated in a single treatment session. Follow-Up and Study Exit will be at 90 Days, Post-Procedure. No repeat ("touch-up") procedures will be permitted during the 90 day follow-up period.
Study Endpoints:	
Primary Endpoint variable(s) – The primary symptom outcome variables include self-reported Nasal Obstruction Symptoms Evaluation (NOSE) score and Visual Analog Scale (VAS) of nasal obstruction. One-way ANOVA with repeated measures will be used to compare post-treatment vs. baseline measurements and determine the effectiveness of the treatment.
 
The primary independent endpoint variables include several categories: 1) variables that index general disease severity (Computerized Tomography (CT) staging and endoscopic examination score 2) peak inspiratory flow measurements of nasal physical resistance.
 
Secondary outcome variables will include age, gender, race, duration of the disease, and medical and smoking histories. The potential confounding effect of the secondary outcome variables will be examined.

Study Evaluations:	
1. Nasal Obstruction Symptoms Evaluation (NOSE) score2. Visual Analog Scale (VAS) of nasal obstruction

3. Endoscopic examination (video and pictures), Lund-Kennedy endoscopic scores
4. Peak nasal inspiratory flow
5. Cone beam CT scan (clinical or research)
6. Sino-Nasal Outcome Test (SNOT-22)
7. Computational modeling of nasal airflow based on CT scan of each visit.

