Study Size: Up to 20 patients meeting the inclusion/exclusion criteria will be recruited.

Anticipated Duration: Enrollment completion/Q2 2019; Follow-Up completion/Q3 2019

Study Visits: Phase 1 - Pre-Admission Evaluation/Patient Consent

Phase 2 – Baseline/Treatment

Phase 3 – Follow-Up 90 Days Post-Procedure / Study Exit

Study Eligibility Criteria:

Inclusion Criteria:

Eligible subjects will meet all the following:

1. Age 18 to 75 years (inclusively)
2. Willing and able to provide informed consent
3. Willing and able to comply with the subject-specific requirements outlined in the study protocol
4. Complaints of nasal obstruction for at least 1 year
5. Failed maximum medical therapy (4-6 weeks of steroids)
6. Nasal Obstruction Symptom Evaluation (NOSE) score of ≥ 60 at Baseline
7. Nasal valve is a primary or significant contributor to the subject's nasal obstruction as determined by the study investigator (based on clinical presentation, physical examination, nasal endoscopy, etc.) and the subject has a positive response to any of the following temporary measures (based on patient history or during office exam):
 - a. Use of external nasal dilator strips (e.g., Breathe Right Strips)
 - b. Q-Tip test (manual intranasal lateralization)
 - c. Use of nasal stents
 - d. Cottle Maneuver (manual lateral retraction of the cheek)

Exclusion Criteria:

Subjects will not be enrolled if they meet any of the following:

1. Prior surgical treatment of the nasal valve
2. Rhinoplasty, septoplasty, inferior turbinate reduction or other surgical nasal procedures within the past three (3) months
3. Severe and/or chronic sinusitis, recurrent sinusitis, or allergies leading to nasal obstruction and currently requiring oral corticosteroid therapy
4. Severe case of any of the following: septal deviation, turbinate hypertrophy, polyps, or ptotic nose tip believed to be the primary contributor to the subject's nasal obstruction symptoms and warranting surgical intervention
5. Known or suspected allergies or contraindications to the anesthetic agents and/or antibiotic medications to be used during the study procedure session
6. Known or suspected to be pregnant, or is lactating
7. Other medical conditions which in the opinion of the investigator could predispose the subject to poor wound healing or increased surgical risk.

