2.0 OVERALL OBJECTIVES

The study will evaluate the outcome of nasal obstruction treated with the Vivaer™ Stylus, and also attempt to use computational aerodynamics simulation and sensory measurements to identify and predict patients' treatment outcome. The ability to envisage variables that will lead to best outcome may have potential to assist patients and clinicians in planning effective, well-informed, personalized treatment/surgery strategies.

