4.0 PROCEDURES

4.1 Research Design

The study will be conducted by the Department of Otolaryngology, The Ohio State University School of Medicine, in conjunction with Aerin Medical. This study is a prospective, case series design, involving a group of patients with chronic nasal obstruction symptoms. The study is a longitudinal design, involving two test sessions: one at baseline (pre-treatment) and one at 90 days post-treatment.

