4.2 Study Size

Up to Twenty (20) patients meeting the inclusion/exclusion criteria will be recruited.

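### A two-visit, before-and-after test in one unblinded, uncontrolled group can show that outcomes changed, but the synopsis and section 4.9 say it will establish that the treatment is effective

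*Combined protocol and SAP*

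**What the plan says.** Section 4.9 (Treatment effectiveness) lists VAS, NOSE, SNOT-22 and peak inspiratory flow, and then states: "One-way ANOVA with repeated measures will be used to compare post-treatment vs. baseline measurements and determine the effectiveness of the treatment". The Study Endpoints row of the synopsis draws the same inference for NOSE and VAS; the test is to "compare post-treatment vs. baseline measurements and determine the effectiveness of the treatment".

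The design is set out elsewhere:

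- Section 4.1: "This study is a prospective, case series design, involving a group of patients with chronic nasal obstruction symptoms", "involving two test sessions: one at baseline (pre-treatment) and one at 90 days post-treatment".
- Section 4.7: "Subjects will have both nasal valves treated in a single study procedure session", so no untreated side is available as a within-subject control.
- Section 4.2: "Up to Twenty (20) patients meeting the inclusion/exclusion criteria will be recruited".
- Section 2.1: the primary symptom outcomes, NOSE and VAS, are self-reported.
- Section 4.8 (Internal Validity) deals only with recruitment.

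The protocol names no sham, untreated, delayed or historical comparator and no performance goal. It gives no significance level for the ANOVA. Section 2.0 adds an attempt to "use computational aerodynamics simulation and sensory measurements to identify and predict" how patients fare after treatment, and hopes this may help in planning individual treatment.

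**The concern.** The plan assigns its test a property that the design does not have. A significant difference between baseline and day 90 says that the mean moved. It does not say why, and nothing else in the design supplies the missing reference.

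At stake is what the trial may conclude. Section 24.5 requires a final report, and section 20.0 has the sponsor keep control of the data for regulatory submissions. If the analysis sentence is followed literally, a small p-value becomes an effectiveness conclusion. A related but narrower issue arises in section 2.0: a factor associated with outcome in a group where everyone was treated may simply mark those who would have improved anyway.

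**Working it through.** The plan gives no power, effect size, SD or significance level, so there is no figure of its own to reproduce.

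**1. Which test it is.** With two time points, the repeated-measures ANOVA has 1 and n − 1 degrees of freedom, and F = t² from the paired t-test. A check on 20 simulated pairs gave 0.01386 for both. The null hypothesis is that the mean change is zero.

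**2. What the mean change contains.** Write mean change = δ + ν, where δ is the device effect and ν is everything else (expectation, natural course, concurrent care). The test responds to δ + ν. No part of the design estimates ν, so when δ = 0 the null is still false whenever ν ≠ 0.

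**3. Illustration.** Assumptions: n = 20 (the stated maximum) and two-sided α = 0.05. Critical t on 19 df is 2.093 and √20 = 4.472, so an observed change of 2.093 / 4.472 = 0.47 SD of the change is already significant. With δ = 0, the probability of a significant improvement is P(T > 2.093), where T is non-central t on 19 df with noncentrality 4.472 × ν/SD.

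| Assumed ν (SD of change) | Noncentrality | P(significant improvement), inert procedure |
|---|---|---|
| 0 | 0 | 0.025 |
| 0.3 | 1.342 | 0.246 |
| 0.5 | 2.236 | 0.564 |
| 0.8 | 3.578 | 0.924 |
| 1.0 | 4.472 | 0.989 |

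With n = 15, the values for 0.3 to 1.0 SD are 0.190, 0.438, 0.821 and 0.949.

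**4. How far this depends on the inputs.** An inert procedure was simulated on the NOSE scale (0–100 in steps of 5, entry at 60 or more as in section 4.3, n = 20, 4,000 trials per setting). Assumed ranges: clinic mean 50–70, SD 15–20, test-retest correlation 0.5–0.9. The share of trials with a significant improvement was:

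| Assumed non-specific improvement | Qualifying NOSE used as baseline | NOSE re-measured after qualifying |
|---|---|---|
| 0 points | 6%–77% (regression to the mean alone) | 2%–3% |
| 5 points | 57%–99% | 18%–87% |
| 10 points | 91%–100% | 55%–100% |

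Which column applies is unclear. Table 1, as extracted, appears to mark NOSE at screening and day 90 only, while the list in section 4.7 includes it among the baseline-visit procedures. The two should be reconciled.

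**5. Other outcomes.** Peak inspiratory flow is less open to reporting bias than NOSE or VAS. As section 4.6 describes it, the result depends on how strongly the subject inhales, and it has no comparator either. Step 2 applies to it unchanged.

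**6. Predictors.** In a single treated group, relating baseline factors to later status is prognosis, and the design supports that. Showing who benefits because of the device needs a contrast with people who did not receive it.

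**The case against.** The plan is open about its design: it is labelled non-randomized and a case series, and the main objective is only to evaluate outcome. The ANOVA is a valid test of mean change, so the complaint is about interpretation. Subjects must have had symptoms for at least a year and have failed medical therapy, which makes spontaneous improvement less likely. Medication changes are recorded and repeat procedures are barred. All of this stands, but none of it supplies a comparator. The plan gives no rule for how medication changes enter the analysis, and the effectiveness wording appears twice without a caveat.

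Three stronger readings are tempting, and the documents do not support them.

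- *An inert device would often pass.* A reader might infer this from the table in step 3. That table is the power curve of any paired t-test at n = 20, under an assumed level and an assumed non-specific change. The protocol states no success rule, and step 4 shows that the rate can be as low as 2%–3% with a fresh baseline and no drift.
- *Season explains the change.* The synopsis gives "Enrollment completion/Q2 2019; Follow-Up completion/Q3 2019" but no enrolment start, so neither the seasonal mix nor the direction of any effect can be worked out.
- *The predictor aim is invalid.* Section 2.0 speaks of an attempt to predict outcome after treatment, which one arm can support as prognosis. Section 4.9 classifies symptom categories and makes no claim about device-specific response. Only the treatment-planning use suggested in section 2.0 goes further than the design.

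**Conclusion.** The point holds for the effectiveness wording in the synopsis and section 4.9. The planned test answers whether the mean changed between baseline and 90 days; it cannot attribute the change to the device. This follows from the design alone and needs no assumed number.

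The probabilities of 25%, 56%, 92% and 99% are illustrative. They rest on n = 20, a two-sided 5% level and non-specific changes of 0.3 to 1.0 SD, none of which the plan fixes. For the predictors, the point is limited to saying that they are prognostic. The matter is worth correcting because it changes what may be concluded, although data collection and conduct are unaffected.

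**What to change.** - **Synopsis and section 4.9:** keep the test if wanted, but replace the effectiveness clause with: *estimate the mean change from baseline to 90 days with its 95% CI; without a comparator this change includes non-specific improvement and is not an estimate of device effectiveness*. With 20 complete pairs the half-width of that interval is 0.47 SD of the change (step 3).
- **Final report (section 24.5):** carry the same limit into the conclusion.
- **Section 2.0:** say that baseline CFD and clinical factors will be examined as prognostic of post-procedure outcome, and that this does not identify who benefits because of the device.

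The cost is wording and a less favourable claim, with no extra patients or procedures. A control arm is not requested. Splitting 20 subjects 10/10 would give about 43% power for an assumed standardized difference of 0.8 (0.8 × √5 = 1.789; 1.789 − 1.960 = −0.171; Φ(−0.171) = 0.43). For 80% power, 2 × (1.960 + 0.842)² / 0.8² = 24.5, that is 25 per arm, would be needed (normal approximation).
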